Analyses will only include concurrently randomised patients. For example, analyses involving comparisons with Regimen A will only include data from patients who were part of the four-arm randomisation. Data from sites that only recruited to three regimens will be excluded from these comparisons, as will data from patients randomised after the change from four to three regimens in sites where this change was made. Details are provided in the Statistical Analysis Plan.

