1.5	5 th Feb 2021	[name]	Combined comments from [name] and Janssen, with responses from [name] Clarification that stratification will prioritise randomisation protocol if small numbers Update to estimands notation for primary endpoint Culture with no identification and <14 days incubation will be excluded (was 7) mPP population added for sensitivity analysis of primary endpoint

			 mortality further sensitivity analyses and PK/PD analyses removed, will be in extensive SAP only
1.6	1 st Apr 2021	[name]	Final comments from Janssen, with responses from [name] after joint meeting changes to definition of TEAEs to align with Extensive SAP.
1.7	13 th May 2021	[name]	Changes after discussion of both SAPs with Janssen. - Clarification of time point for FoR analysis - Not excluding non-assessables from time to unfavourable analysis at Wk132 - New WHO definition of treatment outcomes - Clarification of analysis populations
2.0	14 th May 2021	[name]	Up-versioned as final
2.1	22 nd Sept 2021	[name]	Clarification on wording after programming of primary analyses - Word change: Failure or recurrence (not relapse) - Word change: race not ethnicity - Clarification that randomisation date = day 1 when assigning analysis windows - Clarification that genotypic DST will be used for determination of the mITT population when phenotypic DST is unavailable.
3.0	24 th Sept 2021	[name]	Up-versioned as final (after review by Janssen)
3.1	19 th Nov 2021	[name]	Clarification of wording after double programming.
4.0	22 nd Nov 2021	[name]	Up-versioned as final (after review by Janssen)
4.1	8 th April 2022	[name]	Clarifications in response to feedback from FDA and PPD
5.0	21st April 2022	[name]	Up-versioned as final (after review by Janssen and CIs)
5.1	19 th August 2022	[name]	Clarifications in response to Janssen double programming exercise plus addition of comparison of long-term efficacy and safety for regimen C vs regimen D.
5.2	6 th September 2022	[name]	Incorporating comments from MRC CTU (co- PIs and statisticians) for circulation to Janssen for review.
6.0	9 th September 2022	[name]	Incorporating additional comments from Janssen.

3

GENERAL INFORMATION

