This document describes and substantiates the statistical principles and methods used for the analysis of data from Stage 2 of the STREAM trial. This document is designed to support the STREAM protocol but this Statistical Analysis Plan (SAP) supersedes the SAP as written in the protocol. Every care was taken in the drafting of this SAP, but corrections or amendments may be necessary. A pre-final version (v1.0) of this SAP was signed off before first patient first visit. The final version of the SAP will be signed off before database lock for the primary Week 76 Stage 2 analysis.

The STREAM trial consists of two stages. Stage 1 involves the comparison of two treatment regimens: Regimen A and Regimen B. Stage 2 involves two additional regimens, Regimen C and Regimen D, and makes the comparison between Regimen B and Regimen C for the analysis of the primary endpoint. All treatment regimens are described in detail in the STREAM protocol, Section 2.1.3. Stage 1 and Stage 2 of the STREAM trial each have separate SAPs listed below. Each SAP has differences, but the fundamental statistical principles will be consistent across all SAPs.

Document	Description
Stage 1 SAP	All analyses relating to stage 1
Core Stage 2 SAP	Core analyses for stage 2
Extensive Stage 2 SAP	Expanded analyses for stage 2 supporting CSR

Compliance:

The trial will be conducted in accordance with the ethical principles that have their origin in the Declaration of Helsinki, in accordance with the principles of Good Clinical Practice (GCP) as laid down by the ICH topic E6 (Note for Guidance on GCP), and the applicable regulatory requirements in the participating countries.

Sponsor:

Vital Strategies, f/k/a The International Union Against Tuberculosis and Lung Disease, Inc. [name]

Tel (main): [contact] [contact]

Email: [contact]

Funders:

The United States Agency for International Development (USAID) UK Medical Research Council (MRC) / Department for International Development (DFID) Janssen Research & Development, LLP (Stage 2 only)

Main Contacts:

Co-Chief Investigator

[name] MRC Clinical Trials Unit at UCL Institute of Clinical Trials and Methodology [name]

[contact] [contact] Email: [contact]

Co-Chief Investigator

[name] MRC Clinical Trials Unit at UCL Institute of Clinical Trials and Methodology [name]

[contact] [contact] Email: [contact]

CONTENTS

1	Trial overview	8

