1.6 Randomisation procedure

Patients were initially randomised to Regimen A, Regimen B, Regimen C, or Regimen D, in a ratio 1:2:2:2, respectively. From protocol version 6.3 onwards randomisation to Regimen A and/or Regimen D were restricted or stopped (Table 1).

Randomisation will be stratified by (1) site, (2) HIV status (split into three strata: HIV negative, HIV positive with CD4 count \geq 350 cells/mm³, and HIV positive with CD4 count < 350 cells/mm³).

Table 1: Randomisation according to protocol version

Protocol version	Allocation ratio	Regimens
6.2	1:2:2:2	A:B:C:D
6.3 or 7.0	1:1:1	B:C:D in countries where the local NTP adopted or has imminent plans to adopt the WHO 2016 short regimen; as for v6.0 elsewhere
8.0 onwards	1:1	B:C

All analyses will be stratified by randomisation protocol to ensure comparisons are made to concurrent controls:

- comparisons of Regimen C to Regimen B will include all participants allocated to these regimens but be stratified by a 3 level variable: v6.2 vs v6.3/7.0 vs 8.0/10.0
- comparisons of Regimen D to Regimen B will be restricted to participants randomised under protocol v6.2/6.3/7.0 and be stratified by a 2 level variable : v6.2 vs v6.3/7.0
- comparisons to Regimen A will be restricted to participants randomised under v6.2 of the protocol

Analyses of the primary endpoint will also be stratified by HIV status as defined above, unless there is insufficient data within strata. If this is the case initially the two HIV positive groups will be combined, but if there is still insufficient data within strata then stratification by randomisation protocol will be prioritised.

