7 ANALYSIS OF SECONDARY OUTCOMES

7.1 Efficacy outcomes

Secondary efficacy analyses will be carried out on i) data censored at Week 76, and ii) data from all visits occurring on or before the projected Week 96 visit of the last patient randomised i.e. approximately end of November 2021 (long-term efficacy data). A participant's scheduled last efficacy visit will be their latest scheduled trial visit on or before this date. In addition to the comparisons detailed below, analyses of the long-term efficacy data will include comparisons of Regimen C with Regimen D. Comparisons of Regimen C and Regimen D using data up to Week 76 were carried out at the time of the primary analysis but considered exploratory.

Secondary efficacy outcomes will be analysed on the mITT analysis population with the exception of the analysis of favourable outcome at Week 132 to determine the non-inferiority of Regimen C to Regimen B which will be analysed on the mITT, PP and mPP populations.

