This analysis will be conducted on the whole study period, and separately for follow-up censored at Week 76. It will also be repeated comparing bedaquiline and non-bedaquiline regimens (Regimens A and B vs C and D) and comparing Regimen B_{mox} and Regimen C, and Regimen B_{lev} and Regimen C. A descriptive analysis will consider deaths by cause, as adjudicated by an independent review committee. In addition to the comparisons detailed above, analyses of the whole study period (up to Week 132) will include comparisons of Regimen C with Regimen D. Comparisons of Regimen C and Regimen D using data up to Week 76 were carried out at the time of the primary analysis but considered exploratory.

7.2.3 Proportion of patients experiencing a grade 3 or greater adverse event, as defined by the DAIDS criteria, during treatment and follow-up

The difference in proportion of patients experiencing a grade 3 or greater adverse event, as defined by the DAIDS criteria¹⁰, during treatment and follow-up, between Regimen B and Regimen C, between Regimen B_{mox} and Regimen C, between Regimen B_{lev} and Regimen C, between Regimen B and Regimen D, and between Regimen B and Regimen A, with corresponding two-sided 95% confidence intervals and p-values will be estimated (see Section 6.1.1). The analysis will be stratified by randomisation protocol (as defined in Section 1.6) and HIV status with three strata: HIV negative, HIV positive with CD4 count less than 350 cells/mm³, and HIV positive with CD4 count more than or equal to 350 cells/mm³.

This analysis will be conducted on the whole study period, the study period censored at Week 76, and separately for each phase (Treatment censored at Week 76, and Allocated treatment).

Comparisons will be repeated in subgroups according to HIV infection status. In addition the proportion of participants with cardiac events, hearing loss and hepatotoxicity by Week 76 and Week 132 in Regimen C and Regimen D will be compared to Regimen B.

In addition to the comparisons detailed above, analyses of the whole study period (up to Week 132) will include comparisons of Regimen C with Regimen D. Comparisons of Regimen C and Regimen D using data up to Week 76 were carried out at the time of the primary analysis but considered exploratory.

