8.2 WHO classification of outcome

TB outcome at the end of treatment will be determined using the WHO DR-TB treatment outcomes definition¹¹. Participants will be classified as cured, treatment completed, treatment failed, died, lost to follow-up or not evaluated, with the first two categories considered together as treatment success.

The modified WHO DR-TB treatment outcome definition will also be applied; this includes an additional category of relapse after treatment success, defined as bacteriological relapse after end of treatment cure^{4,12}.

The most recent WHO DR-TB treatment outcome definition¹³ will also be applied; this moves away from bacteriological status and focuses more on the completion of treatment or reasons for incompletion.

Each classification will be tabulated by treatment arm and the unadjusted difference in treatment success comparing Regimen B with Regimen C, Regimen B with Regimen D and Regimen C with Regimen D calculated with 95% confidence intervals.

8.3 **TB outcome irrespective of treatment changes at Week 132**

This analysis will exclude all participants whose scheduled last efficacy visit is before Week 132.

TB outcome will be classified according to the patients' culture status at week 132 regardless of treatment changes or intermediate culture results – similar to a simplistic intention-to-treat analysis.

A participant is defined as "cured at Week 132" if the last two cultures were negative with the last no earlier than the Week 132 analysis window; other categories include death prior to Week 132, last culture positive at Week 132, last culture negative prior to Week 132, last culture positive prior to Week 132, or no cultures after baseline.

This classification will be tabulated by treatment arm, and the difference in proportion cured reported comparing Regimen B with Regimen C, Regimen B with Regimen D and Regimen C with Regimen D calculated with 95% confidence intervals, stratifying for randomisation protocol and HIV status.

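### The long-term C versus D comparisons were added after the Week 76 ones had been run, without their exploratory label, and no C–D population rule secures concurrency in SAP 8.2 and 7.1.4

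*SAP*

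**What the plan says.** **Status.** SAP 7.1, under secondary outcomes, states that "analyses of the long-term efficacy data will include comparisons of Regimen C with Regimen D". The next sentence says that the C–D comparisons on data to Week 76 "were carried out at the time of the primary analysis but considered exploratory". SAP 7.2.2 (mortality) and 7.2.3 (grade 3 or greater adverse events) follow the same pattern: "analyses of the whole study period (up to Week 132) will include comparisons of Regimen C with Regimen D", with only the Week 76 versions called exploratory. None of the 26 secondary objectives in protocol 3.2.2 or SAP 1.2 compares C with D. SAP 7.4 makes no multiplicity adjustment for secondary outcomes.

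**Timing.** The SAP's revision history lists for v5.1 (19 August 2022) the "addition of comparison of long-term efficacy and safety for regimen C vs regimen D". The SAP's general information says: "The final version of the SAP will be signed off before database lock for the primary Week 76 Stage 2 analysis".

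**Concurrency.** Protocol 11.6 says "Analyses will only include concurrently randomised patients". SAP 1.6 says "All analyses will be stratified by randomisation protocol to ensure comparisons are made to concurrent controls" and then gives specific rules for C–B (all participants, three version strata), D–B (v6.2/6.3/7.0 only) and comparisons with A (v6.2 only). It gives none for C–D. SAP 8.2 asks for "the unadjusted difference in treatment success comparing Regimen B with Regimen C, Regimen B with Regimen D and Regimen C with Regimen D". SAP 7.1.4 forms each arm's Week 132 curve as an average over strata, weighted by that arm's own baseline stratum counts.

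**The concern.** There are two separate issues.

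- **Status.** The later comparison, specified when the Week 76 C–D comparisons had already been made, carries a higher apparent status than the earlier one. A reader of the SAP would take it for a planned secondary result.
- **Concurrency.** Randomisation to D stopped with protocol v8.0, while C continued. A C–D estimate that uses every C patient compares D with some patients who could not have been allocated to D. Any change over calendar time in sites, patients or outcome ascertainment then looks like a regimen effect.

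Such a change is plausible. Protocol 1.1.6 reports that several sites closed early. Counting back 96 weeks from end November 2021 puts the last randomisation at about January 2020 and that patient's Week 76 at about July 2021. Under SAP 3.2, a Week 76 sputum missing because of COVID-19 counts as unfavourable, and 7.1.4 carries a Week 76 unfavourable status forward to Week 132.

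**Working it through.** The documents give no sample size, margin, hypothesis or decision rule for C–D, so there is no planned C–D figure to reproduce.

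**1. Timing.** The last patient's projected Week 96 is about 30 November 2021 (protocol 8.1.1). Adding 36 weeks gives 9 August 2022 for the last Week 132. SAP v5.1 is dated 10 days later, and more than 8 months after the efficacy cut-off. No database lock date is given, so the order of events rests on the log date and on the past tense in 7.1, 7.2.2 and 7.2.3.

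**2. Share of C that is non-concurrent.** Inputs: about 100 patients on D (protocol 11.4.3), at least 200 on C (protocol 11.4.1), and C:D of 2:2 under 1:2:2:2 or 1:1 under 1:1:1 (SAP Table 1). Allocation to C and D was therefore equal before v8.0, giving about 100 concurrent C patients. Non-concurrent share = (200 − 100)/200 = 50%. It would be larger if C exceeded 200.

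**3. Where the general rule works.** The Cochran-Mantel-Haenszel weight of a stratum is nC × nD/(nC + nD). Assume the 100 concurrent patients per arm split evenly over the two early version strata:

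| Version stratum | C | D | Weight |
|---|---|---|---|
| v6.2 | 50 | 50 | 25 |
| v6.3/7.0 | 50 | 50 | 25 |
| v8.0 onwards | 100 | 0 | 0 |

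The last stratum gets no weight however the early ones split. It also adds nothing to a C–D log-rank test or Cox model stratified by version. The stratified risk differences for mortality and grade 3 or greater events are therefore already concurrent by protocol version.

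**4. Where it does not: SAP 8.2.** Let the true favourable rate be p in both regimens before v8.0, and p + δ in C patients from v8.0 onwards, with no regimen effect.

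- Crude C rate = (100p + 100(p + δ))/200 = p + δ/2.
- Crude C–D difference = δ/2.
- For an assumed δ of 5 or 10 points, the bias is 2.5 or 5 points.

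**5. Where it does not: SAP 7.1.4, if used for C–D.** Averaging each arm over its own strata puts the v8.0+ stratum into the C curve and not into the D curve. Adjusting the Cox model for version does not undo that. This was simulated with 200 C and 100 D patients, 20% unfavourable before v8.0, no C–D effect and 200 replicates:

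| Assumed δ (points) | Mean C–D difference, all C | Restricted to before v8.0 |
|---|---|---|
| −10 | −5.1 | 0.4 |
| −5 | −1.8 | 0.1 |
| +5 | 3.3 | −0.5 |
| +10 | 4.4 | −0.4 |

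The bias is again close to δ/2, and it is close to zero under the restriction.

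**6. Precision cost of restricting.** 95% half-width = 1.96 × √[p(1 − p)(1/nC + 1/nD)]. At p = 0.80:

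- 200 v 100: 1.96 × √(0.16 × 0.015) = 9.6 points.
- 100 v 100: 1.96 × √(0.16 × 0.020) = 11.1 points.

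Over p from 0.75 to 0.85 the half-width is 10.4 to 8.6 points unrestricted and 12.0 to 9.9 points restricted.

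**The case against.** The strongest reply is that little is left unprotected. Protocol 11.6 and SAP 1.6 both state general concurrency rules, and step 3 shows that stratification enforces them for the added safety risk differences. The SAP dates the addition and discloses beside each added comparison that the Week 76 version had been run. It attaches no confirmatory claim to C–D. The one comparison specified as unadjusted, in 8.2, already falls under the exploratory heading of Section 8, as does 8.3, which is stratified.

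Most of that stands, and it rules out several stronger readings that a reader might infer:

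- **That C–D has no concurrency protection.** It has the general rules; what is missing is a C–D-specific one.
- **That B patients from v8.0 onwards enter the B–D difference in 8.2.** SAP 1.6 already limits every D–B comparison to v6.2/6.3/7.0, and an unadjusted estimator does not lift a population restriction.
- **That 8.2 and 8.3 lack an exploratory label.** Their section heading supplies it.
- **That the Week 76 results prompted the addition.** The documents give no reason for it. They show only the order of events.
- **That 7.1.4 leaves C–D off its list of concurrent comparisons.** The list is garbled in the available text where C and D would appear, so omission cannot be shown.

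The reply does not cover the missing label in 7.1, 7.2.2 and 7.2.3. Nor does it cover 8.2 and 7.1.4, where following the SAP as written would not make the C–D estimate concurrent. The protocol's general sentence is weak cover there, because the SAP states that it supersedes the protocol's analysis section.

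**Conclusion.** The point holds in two limited parts. First, the long-term C–D comparisons in SAP 7.1, 7.2.2 and 7.2.3 were specified after the Week 76 C–D comparisons had been done, and they lack the exploratory label given to those. Second, SAP 1.6 has no C–D population rule, and the general rules do not secure concurrency for the 8.2 C–D difference or for 7.1.4 curves if these are used for C–D.

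About half of the C patients would be non-concurrent in those two places, with a bias of about 2.5 to 5 points. This rests on planning sizes rather than actual enrolment, on equal C:D allocation before v8.0, and on an assumed 5 to 10 point difference in patients from v8.0 onwards, for which the documents give no estimate. The primary C–B analysis and the listed objectives are not affected. This is a cheap improvement.

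**What to change.** 1. In SAP 7.1, 7.2.2 and 7.2.3, label the long-term C–D comparisons exploratory or post hoc, and state the date they were added.
2. In SAP 1.6, add a C–D bullet: restricted to participants randomised under v6.2/6.3/7.0, stratified v6.2 versus v6.3/7.0. Apply that population to the C–D difference in 8.2 and to any C–D analysis under 7.1.4.

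Confine the rule to C–D. A rule for every comparison involving D would conflict with the v6.2-only rule for D–A. It would also remove the B and C patients randomised from v8.0 onwards, who are concurrent with each other, from the pooled mortality comparison of A and B with C and D. Leave those two and the D–B rule as they are.

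The cost is SAP wording and a population filter. Fewer C patients enter the C–D comparisons, with the loss of precision shown in step 6.

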7.1.1 Time to sputum smear and culture conversion

Time to sputum smear conversion is defined as the time from randomisation to the first of two consecutive negative sputum results, collected on separate days. All patients in the analysis population will be included in this analysis, except those with no positive smear result at screening and randomisation. Patients that never achieve smear conversion will be censored at the date of collection of sputum that yielded their last smear result.

Time to sputum culture conversion is defined as the time from randomisation to the first of two consecutive negative culture results, collected on separate days. Patients that never achieve culture conversion will be censored at the date of collection of sputum that yielded their last culture result.

Median time to sputum smear and culture conversion will be calculated for Regimen B, Regimen C, and Regimen D using the Kaplan-Meier estimator.

A hazard ratio with corresponding two-sided 95% confidence intervals and p-value will be estimated for the comparison of Regimen B with Regimen C, and Regimen B with Regimen D.A Cox Proportional Hazards model will be used, adjusted for randomisation protocol (as defined in Section 1.6) and the stratification factor HIV status with the three categories of: HIV negative; HIV positive with CD4 count ≥350 cells/mm³; and HIV positive with CD4 count <350 cells/mm³.

The equality of survivor functions for time to sputum conversion for Regimen B and Regimen C, and Regimen B and Regimen D, will each be tested using a Log rank test, stratified by randomisation protocol (as defined in Section 1 .6) and the randomisation

stratification factor HIV status with the three categories of: HIV negative; HIV positive with CD4 count ≥350 cells/mm³; and HIV positive with CD4 count <350 cells/mm³.

The assumption of proportional hazards between the two comparisons will be tested using the proportional hazards test based on the Schoenfeld residuals after fitting the Cox Proportional Hazards models. In the case where there is adequate evidence that the proportional hazard assumptions are violated at the 5% level (i.e. p<0.05), methods where proportional hazards is not a necessary assumption will be used, such as the Wilcoxon test of equality of survivor functions and restricted mean survival time.

These analyses of time to sputum smear conversion and time to sputum culture conversion will be repeated with the alternative definition as time from randomisation to the first negative culture or smear result respectively (without the need for a second negative culture or smear result to confirm). These analyses will only be carried out on data up to Week 76.

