#### 5.2.2 MDR-TB treatment between screening and randomisation

MDR-TB treatment should not be initiated or continued between screening and randomisation unless clinically necessary or mandated by local policy, and if used may not exceed three weeks.

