5.2 Treatment and follow-up phase definitions

For the purpose of analysis, the treatment and follow-up phases for an individual patient will be defined as follows:

Screening phase

- Start: date of screening consent
- o End: day before randomisation

• Treatment phase

- o Start: date of randomisation.
- End: date of last dose of any TB treatment defined as last dose of any TB treatment (including retreatment for relapse), plus 7 days.

• Follow-up phase

- o Start: the day after the end of the treatment phase.
- End: date of the last patient contact (scheduled or unscheduled visit, or other contact e.g. phone call).

The treatment phase includes any extension of treatment or retreatment, and so the Allocated Treatment phase is defined as follows:

• Allocated Treatment phase

- Start: date of randomisation.
- End: date of last dose of trial treatment defined as last dose of allocated regimen or last dose before the addition of a new drug, whichever happens sooner, plus 7 days.

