Culture results obtained using acidified Ogawa (Kudoh medium) will be used in analysis if available; results from LJ media will be used if the Ogawa result is missing. The only exception to this is within the baseline window, when Ogawa, LJ or MGIT culture results will be considered to determine if a participant is positive at baseline.

Any culture result that is missing because the patient is no longer able to produce sputum will be treated as a negative result, providing their last 2 available culture results (from sputum samples taken at separate visits) are negative.

If more than one culture result is available from sputum collected on the same day, this will be regarded as a single culture result for the purposes of all analyses with the following overall result:

- i. **Positive**, if at least one of the culture results is positive
- ii. **Negative**, if at least one of the culture results is negative and none of the culture results are positive

- iii. **Contaminated** if at least one of the culture results is contaminated and none of the culture results are positive or negative.
- iv. **Missing**, if no culture result is available

5.5 **Definition of culture negative status**

Sputum culture negative status is defined as two consecutive negative cultures from sputa collected on different days without an intervening positive. The date of the first of these negative cultures is the date at which negative culture status is obtained. Culture negative status continues until there are two positive culture results at different visits without an intervening negative culture, or until there is a single positive culture not followed by two negative cultures. Culture negative status can be achieved at any point during treatment or follow-up but before any re-treatment. Culture negative status can be re-established.

5.6 **Definition of a smear result**

A smear result will be called positive if it is graded as 'scanty' or 'rare AFB' or at least 1+. If more than one smear result is available from sputum collected on the same day, this will be regarded as a single smear result for the purposes of all analyses with the following overall result:

- i. **Positive**, if at least one of the smear results is positive
- ii. **Negative**, if at least one of the smear results is negative and none of the smear results are positive
- iii. **Missing**, if no smear result is available.

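### SAP 7.1.1 lets the randomisation-visit sample count as the first negative, so some patients can convert at time zero, with a conditional dilution of the hazard ratio

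*SAP*

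**What the plan says.** SAP 7.1.1 dates culture conversion as "the time from randomisation to the first of two consecutive negative culture results, collected on separate days". For smear: "Time to sputum smear conversion is defined as the time from randomisation to the first of two consecutive negative sputum results, collected on separate days". A repeat analysis on data to Week 76 uses "time from randomisation to the first negative culture or smear result respectively", with no confirming result.

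Three other rules decide whether a Day 1 sample can be that first negative.

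- **Timing.** SAP 5.2 opens the treatment phase with "Start: date of randomisation". SAP 5.5 adds: "Culture negative status can be achieved at any point during treatment or follow-up but before any re-treatment", dated to the first of the two negatives. Protocol 6.1 has sputum collected for smear and culture at the randomisation visit.
- **Population.** SAP 7.1: "Secondary efficacy outcomes will be analysed on the mITT analysis population" (the one exception, Week 132 non-inferiority, is not relevant here). SAP 4.3 admits a patient to mITT on a positive culture at screening or at randomisation. The smear analysis takes everyone "except those with no positive smear result at screening and randomisation".
- **Earlier treatment.** Protocol 5.2.1 allows up to four weeks of second-line treatment before screening. For treatment between screening and randomisation, Protocol 5.2.2 says "if used may not exceed three weeks".

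**The concern.** A patient who is positive at screening, negative at randomisation and negative at Week 4 meets the two-negative definition with an event time of zero. Under the single-negative repeat, the Day 1 result alone is enough. Neither the mITT rule nor the smear exclusion removes this patient.

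A conversion dated to Day 1 precedes any possible effect of trial treatment. If the negative is real, the event says nothing about the regimen, yet it enters the Cox model and log-rank test as a conversion, with equal expected frequency in both arms. At stake are the hazard ratio and power for a listed secondary efficacy outcome, in the B versus C and B versus D comparisons.

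**Working it through.** **No plan figure to reproduce.** The documents give no target hazard ratio (HR), power, event count or number of randomisation-negative patients for this outcome. The size can only be illustrated by simulation.

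**Inputs from the documents.** Sputum at Week 0, then 4-weekly from Week 4 to Week 52, then Weeks 60, 68 and 76, with none at Weeks 1-3 (Protocol 8.1.1). 200 patients per arm (SAP 2.1). For scale only, Protocol 2.2.1 cites HR 2.44 for bedaquiline plus background, with medians of 83 and 125 days: 125/7 = 17.9 weeks, and 125/83 = 1.5 as a lower HR.

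**Assumptions.** Exponential conversion times; control median 8, 10 or 17.9 weeks; Cox model with Efron ties and no covariates; the same share negative on Day 1 in both arms. A Day 1 negative is either *real* (the patient stays negative) or *chance* (unrelated to the later course).

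**Step 1. Two-negative rule, real negatives.** 10,000 per arm, true HR 2.44, control median 8 weeks:

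| Negative on Day 1 | Day 1 counted (as written) | First negative after Day 1 | Positive at randomisation only |
|---|---|---|---|
| 5% | 2.26 | 2.28 | 2.37 |
| 10% | 2.14 | 2.18 | 2.36 |
| 20% | 1.94 | 2.01 | 2.33 |

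With a 17.9-week control median the 10% row is 2.17, 2.19 and 2.39. With 200 per arm and a 10-week median it is 2.19, 2.22 and 2.42, against 2.41 when nobody is negative on Day 1. The small gap from 2.44 reflects the visit grid and simulation error.

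For a true HR of 1.5 (200 per arm, 10-week median, 150 replicates), the rule as written gives 1.47, 1.45, 1.44 and 1.42 at 3%, 5%, 10% and 15%.

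The second and third columns are close because the next sputum after Day 1 is at Week 4. A persistently negative patient simply moves from time zero to Week 4, which is still the first event time and still uninformative. Most of the dilution comes from including these patients at all.

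**Step 2. Power, two-negative rule, real negatives.** 200 per arm, true HR 1.3, 10-week control median, 2,000 replicates:

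- nobody negative on Day 1: about 73%
- 10% negative, as written: about 65% (HR 1.268)
- 10% negative, first negative after Day 1: about 66% (HR 1.272)
- 10% negative, restricted to positive at randomisation: about 69%

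These figures move by a few points with the choice of Cox or log-rank test and between runs.

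**Step 3. Two-negative rule, chance negatives.** Counting or not counting Day 1 changes the HR by less than 0.01. A time-zero event also needs a negative Week 4 result, so it falls on patients who had converted by Week 4 in any case, in proportion to each arm's real rate.

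**Step 4. Single-negative rule.** With chance negatives, Day 1 counted against first negative after Day 1:

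| Setting | As written | After Day 1 |
|---|---|---|
| True HR 2.44, median 8 weeks, 10% | 2.10 | 2.30 |
| True HR 2.44, median 8 weeks, 30% | 1.75 | 2.34 |
| True HR 1.5, median 8 weeks, 10% | 1.43 | 1.50 |

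Power at a true HR of 1.3 with 10% chance negatives is about 67% as written against about 75%. With real negatives the post-Day-1 rule helps little here too: 2.17 against 2.19 at 10%, true HR 2.44, median 17.9 weeks.

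**Step 5. Software.** If the program drops records with time zero, the two-negative HR with real negatives equals the restricted result (2.36 rather than 2.14 at 10%, 8-week median). The SAP does not say which applies.

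**The case against.** The strongest reply is that such patients should be few. Protocol 5.2.1 requires positive FDA vital staining after more than seven days of earlier treatment. Protocol 5.2.2 discourages treatment between screening and randomisation unless it is clinically necessary or mandated locally. Entry needs a positive smear, or a GeneXpert cycle threshold of 25 or lower. At least two samples are taken at randomisation, and under SAP 5.4 any positive makes the day positive. SAP 5.3 also places everything up to Day 1 in a screening/baseline window and opens Week 4 on day 2, which suggests that a post-baseline reading was intended.

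This stands as a reason to expect a small share, and the 3-15% range has no source in the documents. It does not close the gap: 7.1.1 does not tie the event to those windows, and 5.2 with 5.5 points the other way.

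A reader might infer that the conversion hazard ratios are biased in general. The documents do not support that: the effect needs screening-positive, randomisation-negative patients in some number, and under the main definition their negatives must be real and confirmed at the next result. A reader might also infer that a post-Day-1 rule alone restores power. Step 2 shows a gain of about one point. Nor does the gap favour an arm: status before allocation is balanced in expectation, so the pull is towards no difference.

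**Conclusion.** The gap in the definition is real. As written, a conversion can be dated before any trial drug could act, for smear and culture and under both definitions.

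Its size is conditional. At an assumed 10% share:

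- **Single-negative repeat:** diluted whether Day 1 negatives are real or chance.
- **Two-negative main analysis:** diluted only if they are real and persist (true HR 2.44 to about 2.14-2.19; power at a true HR of 1.3 from about 73% to about 65%), and unchanged if they are chance.
- **Either way:** the estimate can turn on an unstated software choice about time zero.

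These figures rest on the assumed share, exponential conversion times and equal shares in both arms. This is a minor point on a secondary outcome. The primary Week 76 outcome does not use time to conversion and is unaffected.

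**What to change.** Add two sentences to SAP 7.1.1, applying to smear and culture and to both definitions:

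1. The first negative must come from sputum collected after the randomisation visit; samples up to and including Day 1 serve only to establish baseline status. This corrects the event date, removes the dependence on how software treats time zero, and recovers most of the loss from chance negatives in the single-negative analysis.
2. A further analysis is restricted to patients positive at randomisation (by smear or culture, as applicable). This is needed because rule 1 barely changes the two-negative hazard ratio; it removes the remaining dilution. If the Day 1 result is missing, the SAP 5.3 baseline rule (use screening) can apply.

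Cost: one date condition and one subset in the program, using data already collected. The downside is a slightly smaller restricted analysis: at 10%, 200 - 20 = 180 per arm, which is why its power is about 69% rather than 73%. If conversion results have already been produced, label the restricted analysis as supplementary.
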